STUDY PROTOCOL (version 2 - 17/09/2024)

Study Title:

The efficacy of different Continuous Glucose Monitoring systems in a cohort of adult patients affected by Inherited Metabolic Disorders prone to Hypoglycemia

Study Type:

Interventional study with CE-marked medical device, single-center, spontaneous

Sponsor:

University Hospital of Padova

Principal Investigator:

[name], MD, PhD

[contact]

Email: [contact]

Coordinating Center:

Division of Metabolic Diseases

Director: [name]

University Hospital of Padova

[name]

Study Background	5
Study Objectives	6
Primary objective	6
Secondary objectives	6
Study Design	6
Study Type	6
Study Site	7
Sample Size Estimation	7
Randomization	7
Statistical method	7
Definition of Analysis Sets	7
Endpoints:	7
Statistical Analysis (example)	8
Observation parameters list (CRF)	8
Study Duration	10
Schematic Study Plan	10
Figure 2. Time design of the study (arrows correspond to a sensor change or a device/system switch)	11
Study Population	11
Inclusion Criteria	11
Exclusion Criteria	11
Study Evaluation	11
Study Quality Control	11
Requirements of Ethics	12
Management Principles	12
Resume	12
Record Storage in the Study Site	12
Protocol Revision	12
Termination of Study Protocol	12
References	13

Abbreviations (examples/alphabetical order)

Abbreviation	Definition
CGM:	continuous glucose monitoring;
CH:	congenital hyperinsulinisms;
FGM:	flash glucose monitoring;
GSD:	glycogen storage disorders;
GV:	glycemic variation;
IMD:	inherited metabolic disorders;
MARD:	mean absolute relative difference;
Rt-CGM:	real time continuous glucose monitoring;
SMBG:	self-monitoring blood glucose;
TAR:	time above range;
TIR:	time in range;
T1DM:	type 1 diabetes mellitus;

Trial Title	The use of Continuous Glucose Monitoring in Inherited Metabolic Disorders prone to Hypoglycemia: Patients' Perspectives and Reliability between Different Devices from an Observational Study
Principal Investigator	[name]
Study Objective/research question	Assessment of perspectives and glycemic reliability of different real time CGM devices in a cohort of adult IMDs patients prone to hypoglycemia
Study Design	Prospective interventional with medical devices CE
Study Population Major Selection Criteria:	Adults affected by Glycogen Storage Disorders and Congenital Hyperinsulinism >18 years; Genetic or biochemical diagnosis of Glycogen Storage Disorder or Congenital Hyperinsulinism, in regular clinical follow up at outpatient services.
Estimated total number of subjects	11
Study Duration	First patient in: 01/01/2025 Last patient out: 01/08/2025

Study Background

Inherited metabolic disorders (IMDs) at risk for hypoglycemia include some rare disorders of intermediary metabolism and metabolic cell signaling (1). Among disorders of intermediary metabolism, Glycogen Storage Disorders (GSDs) are the most relevant, while among metabolic cell signaling congenital hyperinsulinism (CH) is the most frequent.

GSDs are a group of monogenic defects in the synthesis or breakdown of glycogen, with prevalent hepatic and/or muscle involvement, as glycogen is particularly abundant in these tissues (2). The overall estimated incidence of GSDs is 1 case per 20,000-43,000 live births, with over 20 types, including subtypes, and a wide spectrum of clinical presentation (2,3). The management of GSDs is based on dietary treatment, with the goal of maintaining glucose homeostasis and preventing long-term complications; organ transplantation may be an option in some patients (2,3). CH is the most frequent cause of persistent hypoglycemia in pediatric patients. In CH, mutations in 12 different key genes cause inappropriate insulin secretion by pancreatic β -cells, resulting in persistent hypoglycemia (4,5). Moreover, suppressing lipogenesis and ketone body formation during hypoglycemia, CH leads to a higher risk of brain injury. Long-term management in CH involves a combination of pharmacologic therapies and, in cases unresponsive to medical treatments, surgical interventions that may include up to subtotal pancreatectomy (removal of 95–98% of the pancreas) (4). Nutritional management includes frequent feeding with high-caloric carbohydrate feeds, UCCS, and sometimes enteral tube feeding (24/24h or only during the night) (5,6).

In IMDs at risk for hypoglycemia subjects have to control their blood glucose levels to evaluate treatment efficacy. Blood glucose check could be performed through self-monitoring blood glucose (SMBG) by finger stick or through continuous monitoring of glucose concentrations in the subcutaneous tissue. In subjects with type 1 diabetes mellitus (T1DM), Continuous Glucose Monitoring (CGM) is considered a primary standard of care, as it has been shown to improve glycemic control and reduce the frequency of hypoglycemia (7,8). CGM avoids the distress and burden of multiple blood capillary measurements per day; it can also detect glycemic patterns and asymptomatic or overnight hypoglycemia by analyzing recorded glucose level data. Trend arrows suggest future glucose patterns and alarms help in preventing hypo and hyperglycemia (9). In patients with T1DM, glycemic targets have been defined for CGM-parameters (i.e., time in range (TIR) and time above (TAR) and below (TBR) range, glucose variability expressed by coefficient of variation (CV)), and the percentage of TIR has been included in the standard set of person-centered outcomes (10,11).

CGM devices have been divided into two classes based on their characteristics: Real-time CGM (Rt-CGM) and intermittent scanned CGM or Flash Glucose Monitoring (FGM). Rt-CGM gives users the possibility to visualize data in real time on a receiver or smartphone app and it is equipped with alarms (threshold, predictive, or related to arrow trend). FGM reports the user's glucose values when the sensor is scanned by a reader or smartphone app. The first FGM version has not been equipped with alarms, while the second version has been equipped with threshold alarms. Then, the latest FGM version of the App can display real time glucose values.

The actual differences in Rt-CGM systems are in costs, possibility to silence the alarms, number of alarms during the day, selection of pre-set targets, possibility of setting additional alerts, time of sensor duration, only use of smartphone or use of specific receiver.

The role and outcomes of CGM in patients with IMDs at risk of hypoglycemia are still debated by researchers and clinicians expert in the field (9,12–14). However, as CGM has been shown valuable in patients with T1DM to detect unrecognized hypoglycemia and monitor individual glycemic variability (GV), its potential benefit for patients with IMDs is high.

The current IMDs guidelines are cautious about the recommendations on the use of CGM and its clinical practice application in nutritional improvements or modifications (15–17). Rossi et al. have recently proposed indications for CGM monitoring and CGM outcome parameters in patients with hepatic GSDs (14). Peeks et al. also indicated outcome parameters for hepatic GSDs (13).

Worth et al. have recently analyzed the state of art of the evidence for the use of CGM in non-diabetic children with hypoglycemia (9). Some suggestions for qualified CGM use have been provided, but a focus on patients' perspectives on the use of different CGM systems is still lacking, especially on recent tools developed by new technologies.

Study Objectives

Primary objective

Assessment of Pre-set targeted time in hypoglycemia and number of episodes of pre-set hypoglycemia during the different periods of use of CGM tools based on different alarms.

Secondary objectives

Accuracy of the two different CGM systems (comparator SBGM by capillary finger stick).

Assessment of patients' perspectives and tolerance to the use of two subsequent different CGM systems and tools, in particular on different types of alarms: Dexcom One Plus (Dexcom) with threshold alarm and Dexcom G7 (Dexcom) with predictive alarm.

Assessment of quality of life and sleep quality.

Assessment and comparison of glycemic control, patients' perspective and tolerance of CGM with USUAL Care CGM.

Study Design

Study Type

Prospective interventional with medical devices CE

Study Site

Sample Size Estimation

11 IMDs at risk for hypoglycemia

The rare condition of disorders investigated needs to be considered for the sample size (e.g. GSD I has a frequency of approximately 1 in 100,000 and the estimated incidence of CHI ranges between 1:27,000 and 1:50,000 live births in outbred western population).

Randomization

Patients will be randomized to start with the use of Dexcom G7 o Dexcom One Plus after baseline.

Methods for randomization: Randomization will be employed to assign participants to different

Continuous Glucose Monitoring (CGM) systems to ensure unbiased comparisons across the study groups. Simple randomization using computer-generated random numbers will be implemented to allocate patients randomly. This method will help distribute confounding variables evenly between groups, thereby minimizing selection bias. Block randomization may also be utilized to maintain balance in the number of participants among the groups throughout the study. Allocation concealment will be maintained until the intervention assignment to prevent any potential influence on patient enrollment.

Statistical method

Definition of Analysis Sets

The following data sets will be analyzed:

- Full analysis set (FAS):
The set of subjects is as close as possible to the ideal implied by the intention-to-treat principle. All subjects with at least one efficacy follow-up will be included. It is derived from the set of all eligible subjects by minimal and justified elimination of subjects. When handling of missing values of primary outcomes, the last observation carried forward (LOCF) method will be applied.
- Per-protocol analysis set (PPS):
The per protocol analysis set will consist of all patients in the full analysis set plus the following criteria: completion the treatment process, without any major protocol violations, good compliance (80%~120% medical device and capillary finger sticks compliance) and without missing value in primary outcomes. Patients with at least one major protocol violation (e.g missing the 8 weeks efficacy follow up) will be excluded from the per-protocol analysis.
- Safety Set (SS):
The safety set will consist of all subjects followed at least one period with one CGM system.

Endpoints:

Primary: number of episodes of pre-set hypoglycemia (hypoglycemia <70 mg/dL and severe hypoglycemia < 54 mg/dL), time above, under or in pre-set target range, glycemic variations during the different periods of use of CGM tools based on different alarms;

Secondary objectives

Secondary: accuracy and MARD (comparator finger capillary sticks) during the use of two different CGM; perspectives and preferences in monitoring and specific use of different alarms with Dexcom One Plus or with Dexcom G7; correlation of primary endpoint with the quality of sleep, quality of life and/or neurocognitive outcomes i.e. attention, assessed by specific questionnaires; perspectives and preferences in monitoring and specific use of different CGM with Usual Care monitoring.

Statistical Analysis (example)

(1) General Principles

Quantitative variable will be described by the total number of cases, number of missing values, mean, and standard deviation, minimum, maximum and median. Categorical variables will be described by the number of cases and percentages.

All statistical tests will be performed using two-sided test, P value less than or equal to 0.05 will be considered to have examined the difference statistically significant (Unless otherwise noted). For comparison between two groups of the general condition, the suitable method shall be adopted to conduct analysis according to the type of indicators; for the comparison among groups of quantitative data, group t test (homogeneity of variance, normal distribution) or Wilcoxon rank-sum test will be adopted according to the data distribution (the Shapiro-Wilk test will be used beforehand to check whether the variables follow a normal distribution or not); for categorical data, the chi-square test or Fisher's exact test (if the chi-square test is not applicable) shall be adopted; for ordered data, Wilcoxon rank-sum test or Cochran-Mantel-Hansel test shall be adopted. Multiple regression analyses will also be considered, including linear regression for continuous dependent variables, Poisson regression and cumulative logit logistic regression for ordered response variables (or logistic regression for dichotomous variables, such as presence/absence). Moreover, ANOVA or mixed-effects models will be used to compare how the effect of interest varies over time within the same subject, repeated measures.

(2) Completion and Baseline Parameters

The summary of the study completion includes the count of completed cases of each study center, the list of dropout cases, the analysis set description, the comparison of dropout rates of the groups and the list of reasons for incompleteness. The summary of baseline parameters includes demographic characteristics (gender, age, height, vital signs etc.), history of illness and medications, and specific Questionnaires about CGM tolerance, perspectives and expectations. Comparisons among the two different CGM devices groups and gold standard by capillary finger stick will be conducted to evaluate MARD and reliability during the period of observation.

(3) Compliance

- Compliance of study: study compliance to the CGM two medical devices and capillary finger sticks of all groups will be described and compared. A list of subjects with poor compliance (80% below or 120% above compliance) will be generated.

Observation parameters list (CRF)

Patients at screening, baseline, after 30 days of **unblinded monitoring** with Dexcom G7 and 30 days of **unblinded monitoring** with Dexcom One Plus (Fig. 2). The start of the single CGM tool will be randomized (i.e. 50% of patients will random start with G7 and then switch to Dexcom One Plus, and *viceversa*).

- 1) SCREENING _ General data collection: age, gender, height, body weight, minority, career, income, degree of education, family history, smoking habit, primary diseases or accompanied diseases.
- 2) SCREENING _ Previous glucose monitoring (referring to the last 8 weeks): number of capillary fingers sticks per day, use (or not) of CGM and type of CGM device
- 3) SCREENING _ Major comorbidities
- 4) SCREENING _ Document intake of medications
- 5) SCREENING _ Adverse events and the rate of hospitalization during the last year
- 6) BASELINE _ Quality of Life (SF-12 rating scale)
- 7) BASELINE _ Quality of Sleep (Pittsburgh sleep quality index (PSQI))
- 8) FOLLOW UP _ Capillary finger sticks glucose values (3 per day) by diary record

- 9) FOLLOW UP_ CGM values: time above, under or in the pre-set target, number of episodes of pre-set hypoglycemia
- 10) FOLLOW UP_ CGM tolerance, perspectives and expectations (Specific questionnaires)
- 11) FOLLOW UP_ CGM Quality of Sleep (Pittsburgh sleep quality index (PSQI), quality of life (SF12))
- 12) FOLLOW-UP_ Education on the use of CGM device (sensor, receiver or other tools)

Flowchart indicating which parameter is measured when:

Observation Parameters	Screening	Enrollment/Baseline	Follow up - After 30 days	Final Visit study - After 30 days
Informed consent	x			
Demographic (Age, Gender, Career, Degree of Education, Income)	x			
Height	x			
Body Weight	x	x	x	x
Family History	x			
Smoking Habit	x			
Physical exam	x			
Vital signs	x			
Primary Diseases or Accompanied Diseases	x			
Major IMD Comorbidities	x			
Glucometer values		x	x	x
Use of CGM	x			
Documented Intake of Medications	x			
Rate of Hospitalization During the Last Year	x			
Type of CGM Device	x	x	x	x
Capillary finger sticks glucose values (3 per day)		x	x	x
CGM values (time in pre-set hypoglycemia, number of pre-set hypoglycemia, MARD)		x	x	x
Quality of Life Evaluation: SF-12 Rating Scale		x	x	x
Specific Questionnaires for CGM Tolerance, Perspectives, and Expectations		x	x	x
Quality of Sleep: Pittsburgh Sleep Quality Index (PSQI)		x	x	x
Education on the use of CGM device		x	x	x

Study Population

Inclusion Criteria

Adult patients with Glycogen Storage Disease (GSD) or Congenital Hyperinsulinism (CH), aged over 18 years, who have had at least one clinical and biochemical follow-up at the hospital outpatient service within the last year or two years. This includes patients with a biochemical or genetic diagnosis of GSD or CH.

Exclusion Criteria

Inability to sign consent or comply with study procedures. No additional conditions are expected that could introduce bias in the results and therefore require further exclusion criteria.

Study Evaluation

The Ethics Committee of every study site will guarantee the safety of the subjects, receive the effective data and conduct the review on process analysis, and ensure that this study is conducted as per the highest standard of ethics.

Study Quality Control

This study will be conducted by trained and qualified investigators. The investigators shall fill in the CRF in a trustful, detailed and earnest manner to ensure that the content included in the CRF is complete, authentic and reliable. During the study process, the study institution shall conduct examination against case report forms randomly.

Requirements of Ethics

This study complies with the Declaration of Helsinki (version 2000) strictly, and will be conducted as per the relevant medical research regulations and provisions in Italian country.

Before the subjects are included in this study, the investigators are responsible for introducing the purposes, procedures and potential risks of this study to the subjects and their guardians in a complete and comprehensive manner in writing. The subjects have the right to withdraw from this study at any time. Prior to the commencement, it is essential to receive the written informed consent of each subject, which shall be reserved for filing as a clinical research document.

Management Principles

Resume

The latest resume of each investigator and collaborator shall be submitted to the study institution prior to the commencement of this study.

Record Storage in the Study Site

The investigators must preserve all study records, subject-related materials and materials from other sources within the longest period permitted by the hospital. It is recommended that the investigators preserve the study-related materials for 15 years upon conclusion or termination of clinical study.

Protocol Revision

The investigators are prohibited from altering or violating the study protocol at their own discretions. It is approved for implementing the protocol amendment only after discussion and obtaining a written approval or an opinion that such revision is beneficial with signature from the Ethics Committee, unless such revision is necessary to eliminate the danger of patients or only refers to the problems in logic or study management. Any amendment with approval shall be recorded and preserved together with the clinical study protocol after being signed by the investigator and the sponsor.

Any amendment of the clinical study protocol, prior to its implementation, shall have the signature of approval or a signed opinion indicating benefits from Ethics Committee, unless there have the potentials of important safety problems. Under certain circumstances, a revision may be accompanied with the change of the informed consent form. Before implementing the amendment, the investigators must obtain the opinion on the revised informed consent from the Ethics Committee.

Termination of Study Protocol

This study shall be terminated in case of one of the following events:

- (1) The study process violates the protocol substantially;
- (2) According to new studies' evidence, the continuous implementation of this study may endanger the safety of the subjects;
- (3) This study is required to be terminated by health authorities;
- (4) The time to recruit the subjects is far longer than the expected one;
- (5) The principal investigator determines to terminate this study due to safety problems.

If this study must be terminated, the investigators shall make corresponding decisions and inform the Ethics Committee of the results.

References

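### The allocation method is not fixed, and the one firmly stated method, simple randomization, does not secure the planned half-and-half split of starting device in 11 patients

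*Combined protocol and SAP*

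**What the plan says.** The planned total is "11 IMDs at risk for hypoglycemia" (Sample Size Estimation; the synopsis calls the figure estimated). What is randomized is the order of the two devices: "Patients will be randomized to start with the use of Dexcom G7 o Dexcom One Plus after baseline" (Randomization).

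On method, the Randomization section makes two statements:

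- firm: "Simple randomization using computer-generated random numbers will be implemented to allocate patients randomly";
- optional: "Block randomization may also be utilized to maintain balance in the number of participants among the groups throughout the study".

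It gives no block size and no condition under which blocking would be used.

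The section Observation parameters list (CRF) then gives the allocation as a fact: "50% of patients will random start with G7 and then switch to Dexcom One Plus", with the reverse order for the rest.

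Statistical Analysis, General Principles, allows ANOVA or mixed-effects models for repeated measures within a patient. It names no period or sequence term.

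**The concern.** For a single allocation list, simple and blocked randomization are alternatives. A statistician could not build a unique list from this text, and nothing prevents the blocking option from being taken up only after an imbalance has appeared. The stated 50% is also unattainable with an odd number of patients, and the firmly stated method does not secure even the nearest split.

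In a two-period switch design the split between the two orders determines how precisely the device effect can be separated from a period effect. A period effect is plausible here. Monitoring is unblinded, device education is scheduled at baseline and at both later visits, and prior CGM use is recorded as something that may differ between patients at entry. With the sample held at 11 by the rarity of the disorders, avoidable loss of precision is worth preventing. If period is not modelled, an unequal split also moves part of the period difference into the device estimate.

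**Working it through.** **Inputs.** n = 11 (Sample Size Estimation); two orders, G7 first or One Plus first (Randomization; CRF section). Simple randomization is taken as independent draws with probability 0.5, all 11 patients are randomized, and dropout is not modelled. Significance level and sidedness do not enter.

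**The plan's own figure.** The 50% is the expected share under 1:1 allocation, not a result that can be reproduced. Half of 11 is 5.5, so 6:5 is the closest possible split.

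**Formulas for a split a:b, a + b = 11.**

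- Probability, either direction: 2 × C(11, a) / 2^11, where 2^11 = 2048.
- The period-adjusted device effect has variance proportional to 1/a + 1/b = 11/(ab). Relative to 6:5, where ab = 30, the factor is 30/(ab). This assumes equal variance of within-patient differences in the two orders and no carry-over.
- Without a period term the estimate is the plain mean of the within-patient device differences. The period difference enters with one sign in a patients and the opposite sign in b, so the fraction (a − b)/11 remains.

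| Split | Probability | This split or worse | Variance factor | Period difference carried if period is not modelled |
|---|---|---|---|---|
| 6:5 | 924/2048 = 45.1% | 100% | 1.00 | 1/11 = 9% |
| 7:4 | 660/2048 = 32.2% | 54.9% | 30/28 = 1.07 | 3/11 = 27% |
| 8:3 | 330/2048 = 16.1% | 22.7% | 30/24 = 1.25 | 5/11 = 45% |
| 9:2 | 110/2048 = 5.4% | 6.5% | 30/18 = 1.67 | 7/11 = 64% |
| 10:1 | 22/2048 = 1.1% | 1.2% | 30/10 = 3.0 | 9/11 = 82% |
| 11:0 | 2/2048 = 0.1% | 0.1% | not estimable | 11/11 = 100% |

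**Average cost with period in the model,** over the 2046 of 2048 outcomes with both orders filled: (924 × 1 + 660 × 1.071 + 330 × 1.25 + 110 × 1.667 + 22 × 3) / 2046 = 1.12. On the standard error this is √1.12 = 1.06; at 8:3 it is √1.25 = 1.12.

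**With permuted blocks of 2 and 4.** Completed blocks are balanced and fill an even number of places. At 11 patients the last block therefore holds 1 patient (1:0) or 3 of 4 (2:1). Either way the difference is 1, so one unstratified list gives 6:5 or 5:6 with certainty. If recruitment stops at 8, the worst case is a half-filled block of 4 with both patients on the same order: 3 + 2 against 3, or 5:3.

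**With one permuted list of 12 (6 + 6).** This also gives 6:5 at 11. Stopped at 8, it gives 6:2 in 2 × C(6,6) × C(6,2) / C(12,8) = 30/495, about 6% of the time.

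**The case against.** The strongest reply is that the authors saw the issue: the same paragraph names blocking as a means of keeping balance, and if blocks are used the figures for simple randomization do not apply. That is right as far as it goes. It makes this a finding about an unfixed method, not about a method known to be wrong. But an option without block size or trigger secures nothing.

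The second reply is that the loss is modest. This stands. Splits of 7:4 or better make up 77.3% of trials (45.1% + 32.2%), and the average cost is about 6% on the standard error.

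Two stronger readings are tempting, and the documents support neither.

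- A reader might infer that the crossover will usually be badly unbalanced. The miss rate of 54.9% is a slim majority, and most of it is 7:4, at about 7% more variance. Splits of 9:2 or worse occur in 6.5% of trials.
- A reader might infer that imbalance by itself biases the device comparison. It does not. With period in the model, the estimate is unbiased at any split with both orders filled. The 27% and 45% apply only if period is omitted. They are conditional on the realised split (averaged over the randomization the bias is zero), and they are fractions of a period difference that the documents do not quantify. The repeated-measures models in General Principles could accommodate a period term; the plan just does not name one.

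Nor should much be made of the section's remark on confounders. It says only that randomization helps to spread them. A blocked list would not balance covariates at this size either, and every patient uses both devices.

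**Conclusion.** The point holds in a limited form. The Randomization section leaves the method open between a firm statement and an unspecified option, and the firm statement does not secure the split given in the CRF section. Under simple randomization the nearest split, 6:5, is missed in 54.9% of trials, and 8:3 or worse occurs in 22.7%. The consequence is lost precision if period is modelled: about 12% more variance on average, and at least 25% more at 8:3 or worse. If it is not modelled, part of any period difference enters the estimate: 27% at 7:4 and 45% at 8:3, against 9% at 6:5.

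This rests on independent 1:1 draws, all 11 patients randomized, no dropout, no carry-over and equal variances in the two orders. It should be corrected because the remedy is nearly free, not because the expected loss is large.

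**What to change.** 1. **Randomization:** replace the two sentences on method with one rule. Use a single, unstratified, computer-generated list in small permuted blocks, for example sizes 2 and 4 in random order, concealed and prepared by someone who does not enrol patients. This gives 6:5 or 5:6 at 11 patients and stays near balance if recruitment ends early, which matters because slow recruitment is a listed reason for termination. Stratifying by diagnosis would weaken the guarantee: two part-filled blocks could add differences of 2 and 1, which makes 7:4 possible again.
2. **Observation parameters list (CRF):** change the 50% to about half, planned as 6:5 or 5:6.
3. **Statistical Analysis, General Principles:** name period as a fixed effect in the mixed model for the device comparison. Blocking alone does not do this work, since 9% of a period difference remains at 6:5 without it.

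**Cost:** a short amendment covering three places and a new list, before the first patient. The Protocol Revision section requires written Ethics Committee approval unless the change concerns only logic or study management, so the sponsor should settle which route applies. Small blocks make the next assignment slightly more predictable in an unblinded single-centre trial; mixed sizes and concealment limit this. No added patients, visits or procedures are needed.

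### In the full analysis set, LOCF records the first device's result as the second device's result for any patient with a period-1 value and no period-2 value, so that patient's device difference is zero by construction

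*Combined protocol and SAP*

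**What the plan says.** Under Definition of Analysis Sets, the FAS entry rule is "All subjects with at least one efficacy follow-up will be included", and the missing-data rule is "When handling of missing values of primary outcomes, the last observation carried forward (LOCF) method will be applied". Nothing limits the carrying to within a period or within a device.

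The Observation parameters list (CRF) describes 30 days on each device in randomized order: "50% of patients will random start with G7 and then switch to Dexcom One Plus", and the reverse for the others. Its flowchart schedules "CGM values (time in pre-set hypoglycemia, number of pre-set hypoglycemia, MARD") at baseline, at the 30-day follow-up and at the final visit 30 days later. Each device thus has one scheduled summary.

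Under Endpoints, the primary outcomes are hypoglycemia episode counts, time in, above and below range, and "glycemic variations during the different periods of use of CGM tools based on different alarms". The comparison of interest is between device periods.

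The per-protocol set (PPS) requires no missing primary outcome. Its example of a major violation is "e.g missing the 8 weeks efficacy follow up". Statistical Analysis (example) adds that "ANOVA or mixed-effects models will be used to compare how the effect of interest varies over time within the same subject", but does not say that these models replace LOCF.

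**The concern.** In a parallel-group trial, LOCF carries a patient's own earlier value forward under the same treatment. Here the treatment changes between the two follow-up visits. If the second value is missing, the last observation was made under the other device, so the filled-in value is not a measurement of the device to which it is assigned.

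The plan foresees this case. The 8-week follow-up, read as the end of period 2, is its own example of a visit that may be missed. Missing it removes the patient from the PPS but not from the FAS, where LOCF then acts.

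With 11 patients and no power basis, readers will rely on the estimated difference and its precision. A rule that feeds zeros into that difference favours the conclusion that threshold and predictive alarms perform alike.

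**Working it through.** **Inputs from the protocol.** n = 11 (Sample Size Estimation, justified by rarity alone). One CGM summary per device (CRF flowchart). Two-sided level 0.05 (Statistical Analysis: "All statistical tests will be performed using two-sided test, P value less than or equal to 0.05"). No effect size, SD, power or dropout rate is given, so there is no calculation of the plan's own to reproduce.

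**Assumptions made here.** k = 1, 2 or 3 patients with period 1 only; normal within-patient differences with SD 1; dropout completely at random; no period effect; a paired t interval. The true difference is set at 0.94 SD, the value that 11 complete pairs detect with 80% power (noncentral t, two-sided 0.05).

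**Step 1, one patient.** Let Y1 be the period-1 value. LOCF sets the period-2 value to Y1, so the device difference is Y1 − Y1 = 0, whatever the second device would have shown.

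**Step 2, the mean difference.** With true difference δ, the expected estimate is [(11 − k)δ + k × 0]/11 = δ(1 − k/11).
- k = 1: 10/11 = 0.909, diluted by 9%
- k = 2: 9/11 = 0.818, diluted by 18%
- k = 3: 8/11 = 0.727, diluted by 27%

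This does not depend on the paired t assumption. In an unpaired comparison of device groups, the same value enters both means and the dilution is the same.

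**Step 3, simulation (100,000 trials or more), true difference 0.94 SD.** Each cell gives LOCF v observed pairs.

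| k | Mean estimate | 95% coverage | Interval width (SD) | Power |
|---|---|---|---|---|
| 1 | 0.85 v 0.94 | 95% v 95% | 1.30 v 1.39 | 0.75 v 0.76 |
| 2 | 0.77 v 0.94 | 92% v 95% | 1.29 v 1.49 | 0.69 v 0.70 |
| 3 | 0.68 v 0.94 | 87% v 95% | 1.26 v 1.61 | 0.61 v 0.63 |

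At k = 2 the LOCF interval is narrower by 1 − 1.290/1.491 = 0.135, or about 13.5%. With no true difference, the widths at k = 2 are 1.18 v 1.49, and 1 − 1.18/1.49 = 0.21, or about 21%. In that case the LOCF rejection rate is 0.045 to 0.049 for k = 1 to 3, so type I error is not inflated.

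**Step 4, source of the narrowing at 0.94 SD, k = 2.** The half-width is t × SD/√n. The multiplier is 2.228/√11 = 0.672 for LOCF (10 df) and 2.306/√9 = 0.769 for observed pairs (8 df). Their ratio is 0.874, so counting 11 differences instead of 9 narrows the interval by 12.6%. The mean SD is 0.96 v 0.97, which adds only about 1%.

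**The case against.** **Only some dropouts are affected.** A reader might infer that every dropout gets a zero difference. The documents do not support that. A patient who leaves before the first follow-up is outside the FAS. A patient who stops during period 2 may have usable sensor data, and the plan does not state the level at which LOCF works; the visit schedule points to visit level but does not settle it. If period 1 is missing and period 2 is present, the carried value would be the baseline one. That is also not a measurement under the device, but the resulting difference is not forced to zero. All of this stands, and it limits the point to FAS patients with a period-1 value and no period-2 value.

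**A set without LOCF already exists.** The protocol does not name the FAS as the main analysis, and the PPS excludes missing primary outcomes. This stands too. However, the PPS also excludes for compliance and protocol violations, so it does not isolate the effect of LOCF.

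**The test decision hardly changes.** Correct: type I error does not rise, and power at k = 2 is 0.69 v 0.70.

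**The interval figures rest on a method that the plan does not name.** Also correct. Statistical Analysis lists a group t test, rank-sum tests, regression, and ANOVA or mixed models, and mentions no confidence interval. With the unpaired t test and an assumed within-patient correlation of 0.5 to 0.8, coverage at k = 2 or 3 is 98% or more and the interval does not narrow. Only the k/11 dilution carries over.

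**The zeros need not shrink the SD.** At 0.94 SD they leave it almost unchanged. At 1.5 SD with k = 2 they raise it (1.07 v 0.97).

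**Conclusion.** Wrong as written. The FAS rule assigns one device's result to the other for any patient with period 1 only, and no other text in the protocol prevents it. Naming mixed-effects models does not help if they are fitted to LOCF-filled data.

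The firm part is arithmetic: the device difference is diluted by k/11, so each such patient costs about 9% of the effect. It rests on LOCF acting at visit level and on k being above zero. The coverage and width figures are illustrations under the stated assumptions. The 21% narrowing applies only when there is no true difference, and should not be read together with the coverage of 92%, which belongs to a true difference of 0.94 SD.

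A reader might go further and infer false-positive findings or a marked loss of power. The calculations show neither.

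**What to change.** Delete the LOCF sentence from the FAS definition and state that no value is carried across periods or devices. Then specify:

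- **Model.** Analyse all observed patient-periods in the FAS with the mixed-effects model type that Statistical Analysis already names, with fixed terms for device, period and sequence and a random patient effect.
- **Time measures.** Express time in, above and below range as a percentage of the sensor time actually recorded in that period.
- **Episodes.** Analyse counts as a rate, with a count model and the log of recorded time as offset. A percentage of sensor time does not deal with counts.
- **Sensitivity analysis.** Report complete pairs from the FAS, separately from the PPS.

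The cost is a few sentences rather than one, because the protocol does not yet specify the model terms. The interval will be somewhat wider when patients drop out: 1.49 rather than 1.29 SD in the k = 2 illustration. That wider interval reflects the data actually observed.
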